#### 4.8.4 Other Efficacy Analyses

No imputation for missing data is used for Other Efficacy variables, i.e. only observed data are presented, except for laboratory results reported as below the lower detection limit (or reported above a specific value) which will be imputed as described in [Section 4.2](#).

##### 4.8.4.1 Peanut-specific IgE and IgG4 over time

Descriptive analysis of peanut-specific IgE and IgG4 over time including actual values, absolute and relative changes from Baseline at Month 3, Month 6 and Month 12 will be provided for the overall ITT population and by screening ED subgroup.

Repeated-measures ANCOVA models will be built to compare the mean absolute change from Baseline value in peanut-specific IgE and IgG4 using all time points evaluated up to M12 in the active Viaskin® Peanut 250 µg group versus the placebo group on the ITT population using observed data. The possibility of running the model on log10-transformed data will be investigated. The repeated-measures ANCOVA model will be run globally and for each screening ED subgroup. Treatment group, treatment-by-time point interaction, Baseline value and screening ED subgroup (only for the model run on the global ITT population) will be included in the model.

The SAS® code used is listed in [Appendix 2.4: Statistical analysis methods](#) and procedures used for the analysis over time of peanut-specific IgE and IgG4.

Statistics reported will include: Adjusted Least Square (LS) Mean and standard error of the absolute change from Baseline at each time point (Month 3, 6 and 12), together with the LS mean difference versus Placebo, the associated 95% confidence interval and the corresponding p-values at each time point. P-value for treatment effect all time points taken together will also be provided.

Mean (±SD) and median relative (+/- IQR) change from Baseline in IgE and IgG4 will be presented graphically, by treatment group, for the overall ITT population as well as for each screening ED subgroup.

The log10 transformation of the ratio between peanut specific IgG4 and peanut specific IgE, calculated as:

$$\log_{10} \left( \frac{\text{Peanut specific IgG4 (mg/L)} \times 1000}{\text{Peanut specific IgE (kU/L)} \times 2.4} \right)$$

will be tabulated for the ITT population at each time point:

- by treatment group and overall;
- for each screening ED subgroup;
- for the 2 age subgroups: 4 to 5 years-old; 6 to 11 years-old;
- for treatment responders vs. non responders (primary endpoint), by treatment group and overall.

For patients treated with Viaskin® 250 µg:

- The association between change in cumulative reactive dose and the log10 of the ratio will be evaluated through an ANCOVA (SAS® MIXED procedure) with cumulative reactive dose as the outcome and the log10 ratio as the single factor.

- The association between treatment response and the  $\log_{10}$  of the ratio will be evaluated through a generalized linear model (SAS® GENMOD procedure) with treatment response as the outcome and the  $\log_{10}$  ratio as the single factor.

#### 4.8.4.2 Skin prick test mean wheal diameters over time and at Month 12

Descriptive analysis of SPT mean wheal diameter over time including actual values and absolute change from Baseline at Month 3, Month 6 and Month 12 will be provided for the overall ITT population and by screening ED subgroup.

The mean wheal diameter at M12 in each treatment group will be compared using an analysis of covariance (ANCOVA) model on the ITT population on observed data. The ANCOVA model will be run globally and for each screening ED subgroup. The model will include the treatment group, adjusted for the Baseline value and the screening ED subgroup (only for the model run on the global ITT population) as covariates.

The process followed for the analysis and the SAS® code used will be the same as the one described in 4.8.3.3.

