- If the DBPCFC is stopped without the objective symptoms leading to ending the DBPCFC (stopping rules) or if the subject took the 2,000mg dose without any objective symptom leading to ending the DBPCFC, the CRD value at M12 is considered as the maximum between:

- r the sum of all doses given at Month 12, including also the repeated and partial doses AND
- r the CRD value at screening

- For the subjects who did not undergo the M12 DBPCFC, CRD at screening is carried forward at M12.

- On the FAS and on the PP population (using observed data)

- If the M12 DBPCFC is stopped without any objective symptoms leading to ending the DBPCFC (stopping rules) or if the subject took the 2,000mg dose without any objective symptom leading to ending the DBPCFC, the CRD at Month 12 is considered as the sum of all doses given at Month 12, including also the repeated and partial doses.

The peanut protein cumulative reactive dose in each treatment group at M12 will be compared using an analysis of covariance (ANCOVA) model. The ANCOVA model will include the treatment group, adjusted for the Baseline cumulative reactive dose value. This comparison will be performed in the overall ITT population using mBOCF imputation [Number 4 in the pre-defined hierarchical order of the efficacy analyses], as well as for each screening ED subgroup [Number 10 & 12 in the pre-defined hierarchical order of the efficacy analyses].

Additionally, this analysis will be repeated on the FAS and the PP population, using observed data, overall and for each screening ED subgroup.

Finally, the M12 peanut protein cumulative reactive dose comparison will also be performed for each age group (4-5 and 6-11 years of age):

- On the overall ITT population (using mBOCF imputation),
- On the FAS (using observed data),
- On the PP population (using observed data).

The ANCOVA will be performed through a mixed procedure. A sample of the SAS® code to be used can be found in [Appendix 2.3: Statistical analysis methods and procedures used for the analysis of the cumulative reactive dose of peanut protein at month 12.](#)

The following statistics will be presented:

- The Least square means (LS Means) by treatment group: mean for the variable obtained by the model adjusted on the covariates
- The difference between the LS Means and the associated confidence interval

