### **Appendix 2.3: Statistical analysis methods and procedures used for the analysis of the cumulative reactive dose of peanut protein at month 12.**

The following notations in minor case will be used in the SAS® code lines provided below:

Crd0(12) = Variable for Peanut protein cumulative reactive dose at Baseline (M12)
 
trt = Binary variable for study treatment

---

- The peanut protein cumulative reactive dose in each treatment group at M12 will be compared using an analysis of covariance (ANCOVA) model. The ANCOVA model will include the treatment group, adjusted for the Baseline value.

```
PROC MIXED ;  
CLASS trt;  
MODEL crd12=trt crd0 / DDFM=KR ;  
LSMEANS trt / CL DIFF OM ;  
ODS OUTPUT LSMEANS=<least square means>  
DIFFS=<least square means differences> ;  
RUN ;
```

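### SAP 4.8.4.1 sets out to relate change in cumulative reactive dose to the IgG4/IgE ratio, but specifies the dose itself as outcome, no baseline terms and no time point for the ratio

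*SAP*

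**What the plan says.** SAP 4.8.4.1 defines a log10 ratio of peanut-specific IgG4 to IgE, which "will be tabulated for the ITT population at each time point". Two association models follow, restricted to the active arm ("For patients treated with Viaskin"). The first is introduced as "The association between change in cumulative reactive dose and the" log10 ratio. The model given for it is an ANCOVA in PROC MIXED, "with cumulative reactive dose as the outcome and the" log10 "ratio as the single factor". The second begins "The association between treatment response and the" log10 ratio and is a generalized linear model, again with the ratio as the only term.

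The main CRD comparison in SAP 4.8.3.3 is specified differently: "The ANCOVA model will include the treatment group, adjusted for the Baseline cumulative reactive dose value". The Appendix 2.3 code agrees: "MODEL crd12=trt crd0 / DDFM=KR". Appendix 2 has no code for the association models, and SAP 4.13 does not mention them.

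**The concern.** Change in CRD and CRD are different quantities, and SAP 4.8.3.3 tabulates them separately. The sentence in 4.8.4.1 names one as the target and the other as the outcome, and nothing elsewhere says which is meant. Two programmers could fit different models and both claim to follow the SAP.

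The missing baseline terms matter under either reading. Month 12 CRD partly carries forward baseline CRD, and the Month 12 ratio partly carries forward the baseline ratio. If the two are correlated at screening, they will be correlated at Month 12 even when what happened during treatment is unrelated. With the active arm alone in the model, no placebo slope is fitted to show how much of the association was there beforehand. What is at stake is the interpretation of one supporting analysis: whether a movement in the ratio goes with a movement in the reactive dose.

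**Working it through.** The plan gives no power or sample size for this analysis, so there is no figure to reproduce. The check asks what the stated model estimates when change in ratio and change in CRD are unrelated.

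**Inputs from the documents.** Active arm 220 and drop-out up to 15% (SAP 4.12): 220 × 0.85 = 187. Entry-challenge steps 1, 3, 10, 30, 100 and 300 mg (protocol 6.1.1.2), so nominal baseline CRD is 1, 4, 14, 44, 144 or 444 mg. Expected active response 60% in stratum 1 (73 active children) and 30% in stratum 2 (146) (SAP 4.12).

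**Assumed inputs, not in the documents.** Baseline ratio–CRD correlation ρ; ratio stability s and CRD tracking t from baseline to Month 12.

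**Step 1: the model as written, with the Month 12 ratio.** On standardised scales let R12 = s·R0 + noise and C12 = t·C0 + independent noise. Then corr(R12, C12) = s·t·ρ. Take s = 0.8 and t = 0.5. Approximate power at n = 187 comes from z = atanh(r)·√184.

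| ρ | r = 0.4ρ | r² | z | Power by formula | Simulated (4,000 trials) |
|---|---|---|---|---|---|
| 0 | 0 | 0 | 0 | 5% | 5% |
| 0.2 | 0.08 | 0.6% | 1.09 | 19% | 19% |
| 0.3 | 0.12 | 1.4% | 1.64 | 37% | 38% |
| 0.5 | 0.20 | 4.0% | 2.75 | 79% | 79% |

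**Step 2: sensitivity to the assumptions.** A second simulation used the protocol dose ladder, with assumed SDs on the log10 scale of 0.7 (threshold), 0.6 (its change), 0.5 (ratio) and 0.35 (its change). These imply s = 0.5/√(0.5² + 0.35²) = 0.82 and t = 0.7/√(0.7² + 0.6²) = 0.76, so r is about 0.62ρ. Rejection on log10 CRD was 5%, 13%, 37%, 69% and 92% at ρ = 0, 0.1, 0.2, 0.3 and 0.4. On raw mg it was 5%, 11%, 31%, 58% and 83%. The higher rates come mainly from the stronger CRD tracking.

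**Step 3: change as outcome, ratio still alone.** In the second simulation this gives 4–6% on the log10 scale, but 9%, 25%, 48% and 74% on raw mg at ρ = 0.1 to 0.4. Under Step 1's inputs, C12 − C0 = −0.5·C0 + noise and its variance is 1 + 1 − 2(0.5) = 1, so corr(R12, C12 − C0) = −0.8 × 0.5 × ρ = −0.4ρ. The spurious association has the same size with the opposite sign. Changing the outcome alone is therefore not a reliable remedy.

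**Step 4: baseline terms added.** With baseline CRD only, the second simulation gives 4–6% (log10) and 5–9% (raw mg). With baseline CRD and baseline ratio, it gives 4–5% on both scales. Under Step 1's inputs, a change-on-change model adjusted for both baselines gives 4–6%.

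**Step 5: if the baseline ratio is meant.** Then corr(R0, C12) = t·ρ = 0.5ρ, or 0.10 and 0.15 at ρ = 0.2 and 0.3. Baseline CRD is still needed.

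**Step 6: responder model.** Assume no link between ratio and response within subgroup, and a 0.5 SD difference in ratio between ED subgroups. Covariance is (1/3)(2/3)(0.30)(0.5) = 0.033. The SD of response is √(0.4 × 0.6) = 0.49 and the SD of the ratio is √(1 + (2/9)(0.25)) = 1.03, so r is about 0.07. Simulated rejection (219 children, linear-probability test) is about 17% without the subgroup term and 5% with it. At a 0.25 SD difference it is 7% without.

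**The case against.** The outcome wording may be a drafting slip, since the same sentence states the target as change. That stands as a possibility. It removes the mismatch but not the missing baseline terms, and Step 3 shows that change alone is not safe. SAP 4.2 calls for log10 transformation of non-normal data. That helps under the second set of assumptions, but the sign reversal under the first does not depend on the mg scale.

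The rejection rates are not false positives for the stated model. They are its power to detect a real, small association between levels, and are misleading only for the question about change. That is correct, and it limits what the percentages show.

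A reader might infer that the plan will produce a spurious treatment biomarker. The documents do not support this. The SAP promises an association and claims neither a biomarker nor mediation. Protocol 8.5.4 makes p-values for the other efficacy endpoints descriptive, and the analysis is not among the 14 steps of SAP Table 2. SAP 4.8.4.1 also tabulates the ratio at each time point by response status and treatment group, so pre-treatment differences by response, and the placebo arm, will be visible. That tabulation does not cover CRD.

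A reader might also carry the tolerance argument straight over to the responder model. It does not transfer directly: the response threshold rises with screening ED (SAP 4.8.2), and the expected active response is higher in the more sensitive stratum. The reason to adjust there is the subgroup difference in Step 6.

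**Conclusion.** The point holds as a specification gap in a descriptive analysis. The text states a question about change, gives a model for level, omits both baselines and leaves the ratio's visit open. Followed literally, it cannot separate a shared shift during treatment from differences between children that were present at screening.

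How much this matters is unknown. It is nil if ratio and CRD are uncorrelated at baseline. At correlations of 0.2 to 0.3 it gives about 19% to 38% rejection under the first set of assumptions and 37% to 69% (log10 CRD) under the second, all with 187 children and the Month 12 ratio. The associations concerned are small, about 1% of variance under the first set. The baseline correlation, stability and tracking are all assumed, so these are ranges and not predictions. No primary or secondary conclusion, and no type I error statement, depends on this analysis.

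**What to change.** In SAP 4.8.4.1:

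- Name the outcome as Month 12 CRD or its change, on the log10 scale, with baseline CRD as a covariate.
- State the visit at which the ratio is taken. If it is Month 12, add the baseline log10 ratio, or use change in ratio plus baseline ratio. If it is baseline, say that this is a predictor analysis; baseline CRD still belongs in the model.
- Add screening ED subgroup to the responder model, because the response definition and the expected response rates differ by subgroup.

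All these variables are already scheduled at Visit 1, in the entry challenge and at Month 12, so the cost is a few words of text and two or three covariates. The downside is that children without paired baseline and Month 12 immunology samples drop out of any model that uses both.

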#### 4.8.4.3 Descriptive analysis of the quality of life questionnaires (Food Allergy Quality of Life Questionnaire [FAQLQ]/Food Allergy Independent Measure [FAIM]) and change from Baseline at Month 12.

##### Food Allergy Quality of Life Questionnaires (FAQLQ)

The FAQLQs (Child Form [CF] and Parent Form [PF]) are disease-specific health-related quality of life questionnaires for subjects with food allergy.

At screening and at M12, the following questionnaires will be completed (for countries where translated and validated questionnaires are available and used):

By subjects, for subjects  $\geq 8$  years of age (at screening):

- FAQLQ-CF: 24 items,

By parents for all subjects:

- FAQLQ-PF: 26 items for subjects aged 4 to 6; 30 items for subjects age 7 and older (at screening),

Age at screening will be used to define which items will be applicable during the study for each subject. Items not applicable will be not used for analysis. The sub-scores rely on different numbers of items according to the age-groups (4-6 and 7-12 years old).

FAQLQ questionnaires will be summarized on specific scores calculated by main domains of quality of life. FAQLQ-CF will be analyzed according to the 4 following domains [1]:

- EI: Emotional impact (item no: 19-24),
- AA: Allergen avoidance (item no: 4, 6-10, 15),

- RAE: Risk of accidental exposure (item no: 11, 13-14, 16-17),
- DR: Dietary restriction (item no: 1-3, 5, 12, 18).

FAQLQ-PF will be analyzed according to the 3 following domains [2]:

- ⌘ EI: Emotional impact (item no: 2, 6-7, 9-11, 23-28, 30),
- ⌘ FA: Food-related anxiety (item no: 1, 4-5, 16-17, 20-21, 29),
- ⌘ SDL: Social and Dietary limitations (item no: 3, 8, 12-15, 18-19, 22).

The following instructions from the reference website (www.faqlq.com) will be used for the derivations of (sub-) scores:

- 1) Each question of the FAQLQ is answered on a 7-point scale (0 to 6) and should be recoded 1 to 7. (Note: FAQLQ-CF items are coded on a scale of 1-7 in the CRF and in SDTM)
- 2) The total FAQLQ-scores (except for FAQLQ-PF for which the total score is equal to the sum of the three-scores score divided by 3) and all sub-scores are calculated by dividing the sum of completed items by the number of completed items
- 3) If > 20% of items in any (sub-)domain are missing then the respective (sub-)score is set to missing

Baseline and Month 12 values for each item of the FAQLQ questionnaires will be summarized overall and by treatment group, in the ITT population.

Baseline, Month 12 and change from Baseline of the the FAQLQ scores (global score, scores by domain) will be summarized overall and by treatment group, in the ITT population.

The scores range from no problem/impairment to maximal problem/impairment. A negative score in the changes from baseline means impairment.

Additionally, an ANCOVA model will be built to test the change from Baseline in FAQLQ scores between treatment groups. The model will include the treatment group, adjusted for the Baseline value and the screening ED subgroup as covariates.

Baseline, Month 12 and change from Baseline of the FAQLQ questionnaires (global score, scores by domain as well as values for each item of the questionnaires) will also be summarized using descriptive statistics by response status (Responder/Non responder), in the ITT population.

Finally, the change in FAQLQ scores according to the change in cumulative reactive dose will be assessed graphically (for the global score and each domain specific score).

FAQLQ data will be listed.

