#### **8.5.4 Other Efficacy Analyses**

No further adjustments will be made for the other efficacy endpoints for which p-values will be provided for descriptive purpose only. The following efficacy analyses will be performed using observed data (no imputation will be done).

- Peanut-specific IgE and IgG4 analysis over time: Peanut-specific IgE and IgG4 levels at baseline and changes from baseline to Months 3, 6 and 12 will be summarized descriptively by treatment group on the whole ITT population and for each screening ED stratum, using observed data. Besides, the peanut-specific IgE and IgG4 results at Month 12 will be compared for the whole ITT population and for each screening ED stratum using an ANCOVA model on observed data. The ANCOVA model will include the treatment group, baseline value, screening ED stratum, and region (Australia/Europe/North America) as covariates. Results will be log-transformed if needed.
- Skin Prick Test analysis: The mean change from baseline at Months 3, 6 and 12 in maximum average wheal diameter will be evaluated for each treatment group on the whole ITT population using observed data. The SPT results at Month 12 will be compared for the whole ITT population using an ANCOVA model on observed data. The ANCOVA model will include the treatment group, baseline value, screening ED stratum, and region (Australia/Europe/North America) as covariates. Results will be log-transformed if needed.

A quality of life score from the FAQLQ/FAIM will be summarized at Month 12 and compared to baseline for both treatment groups for the overall ITT population, using observed data.

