## 4.2 General Considerations

The following conventions will be used when presenting summary statistics and analyzing continuous study data:

- Continuous data will be summarized in terms of number of subjects or observations with non-missing data (n), mean, standard deviation (SD), first quartile (Q1), median, third quartile (Q3), minimum (min) and maximum (max), unless otherwise stated.
- For data not normally distributed, a  $\log_{10}$  transformation will be implemented before analysis.
- Compared to the number of decimals recorded for the raw data in the database, the statistics will be reported with the following number of decimals:
  - Minimum and maximum: same number
  - Mean, median, Q1, Q3: one extra decimal
  - Standard deviation: two extra decimals.
- For any parameter at a specific visit:
  - Change from Baseline will be calculated as the value of that parameter at that visit minus the Baseline value of that parameter
  - Relative change from Baseline will be calculated as the value of that parameter at that visit minus the Baseline value of that parameter divided by the Baseline value of that parameter
- For laboratory parameters, values below a detection limit or above a specific value (e.g.  $<0.35$  kU/L or  $>100$  kU/L) will be considered as equal to that limit/value (e.g.  $=0.35$  or  $100$ ) in the statistical analyses (except in listing where the reported value will be presented).

In case of change of detection limit during the course of the study (e.g. from  $<0.35$  kU/L to  $<0.1$  kU/L), all values lower than the highest limit value will be imputed to this threshold (e.g. all values lower than  $0.35$  kU/L will be considered as equal to  $0.35$  kU/L). This conservative approach will ensure that changes from Baseline are consistent.

The following conventions will be used when presenting summary statistics for categorical study data:

- Categorical data will be summarized in terms of the number of subjects or observations providing non-missing data at the relevant time point (n), frequency counts and percentages. Any planned collapsing of categories will be detailed in the SAP text and the data displays.
- Percentages will be presented to one decimal place. Percentages will not be presented for zero counts. Percentages will be calculated using n as the denominator. If sample sizes are small, the data displays will show the percentages, but any textual report will describe frequencies only.

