#### Food Allergy Independent Measure (FAIM)

The FAIM questionnaires capture the subject's expectation of something happening because of her/his food allergy.

Each item of the FAIM is answered on a 7-point scale (0 to 6) and should be recoded 1 to 7.

Total FAIM scores will be calculated by dividing the sum of completed items by the number of completed items. Total FAIM scores range from 1 "low perceived disease severity" to 7 "high perceived disease severity".

Calculation of total FAIM scores will be done only when 80% or more of the items are completed.

Some specific items as mentioned below have to be reversed:

- FAIM-CF: Child Form (8-12 years)  
This questionnaire consists of 6 items. The mean score will be performed if at least 5 items are completed.
  
- FAIM-PF: Parent Form (Children aged 0-12 years)  
There are 2 sections given in the questionnaire each with the same items :
  - one from the perspective of the parents (What chance do you think your child has of.....?)
  - one reflecting the thoughts of the child (What chance does your child think he/she has of.....?).

Both mean scores of the parent's form ("Parent's thoughts" and "Child's thoughts") are calculated as the mean of the single items, only if none of the items is missing. In both scores item 4 needs to be reverse scored.

Baseline and Month 12 values for each item of the FAIM questionnaires will be summarized overall and by treatment group, in the ITT population.

Baseline, Month 12 and change from Baseline of the FAIM questionnaires (global score, scores by domain) will be summarized overall and by treatment group, in the ITT population.

Baseline, Month 12 and change from Baseline of the FAIM questionnaires (total score, as well as values at each item of the questionnaires) will also be summarized using descriptive statistics by response status (Responder/Non responder), in the ITT population.

FAIM data will be listed.

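### SAP 4.8.4.3 reads the sign of FAQLQ change backwards: on the SAP's own scale and change formula, a negative change is improvement, not impairment

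*SAP*

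**What the plan says.** SAP 4.8.4.3 sets out how the FAQLQ is scored and analysed. On item coding it says "Each question of the FAQLQ is answered on a 7-point scale (0 to 6) and should be recoded 1 to 7", and it adds that Child Form items already carry codes 1 to 7 in the case report form and the SDTM data. On aggregation, "sub-scores are calculated by dividing the sum of completed items by the number of completed items". The Child Form total is built the same way, and the Parent Form total is the mean of its three domain scores.

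On direction, the section says "The scores range from no problem/impairment to maximal problem/impairment". The next sentence is the one at issue: "A negative score in the changes from baseline means impairment".

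The definition of change is in SAP 4.2 and covers any parameter at a given visit: "Change from Baseline will be calculated as the value of that parameter at that visit minus the Baseline value of that parameter". Neither the protocol nor the SAP gives a different formula for FAQLQ.

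SAP 4.8.4.3 then uses the change scores in three ways: an ANCOVA comparing arms, descriptive summaries by responder status, and plots against change in cumulative reactive dose.

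**The concern.** Two adjacent sentences in the same section cannot both hold once the SAP 4.2 formula is applied. If high scores are bad and change is Month 12 minus Baseline, a fall in score is good news. The SAP says it is bad news.

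This is the only place in either document that says outright what the sign of an FAQLQ change means, so it is the sentence that someone writing a table footnote or the results text would be expected to follow. Applied as written, a quality-of-life benefit of active treatment would be reported as harm, and a harm as benefit. In the ANCOVA, a negative active-minus-placebo difference in change favours active treatment, and the rule would turn that round. The responder and non-responder summaries and the dose plots would be misread in the same way.

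**Working it through.** This is a check of sign. The plan gives no figure to reproduce.

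**Inputs**

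- Parent Form anchors (protocol Appendix 7): 0 is no impact on the child's quality of life and 6 is an extreme impact.
- Child Form labels (protocol Appendix 7): ordered from none to extreme, with no numeric codes printed on the form.
- Coding (SAP 4.8.4.3): 0 to 6 becomes 1 to 7, in the same order.
- Scores (SAP 4.8.4.3): item means. The Parent Form total is the mean of three domain scores.
- Change (SAP 4.2): visit value minus Baseline.

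**Step 1. Recoding cannot alter the sign.** Let *a* be the raw Baseline value and *b* the raw Month 12 value. After recoding, the change is (b + 1) - (a + 1) = b - a. Child Form items are stored as 1 to 7 already, so no shift is needed there.

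**Step 2. Aggregation keeps the direction.** A mean of items that all point the same way points that way too, and so does a mean of domain means. The domain lists use each of the 24 Child Form items once and each of the 30 Parent Form items once, and none is reversed.

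**Step 3. Numbers.** Set every item to the same raw value. The result is the same for the Child Form total and the Parent Form total:

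| Raw Baseline to Month 12 | Score Baseline to Month 12 | Change | Actual meaning | Under the SAP sentence |
|---|---|---|---|---|
| 4 to 2 | 5 to 3 | 3 - 5 = -2 | less impairment | impairment |
| 6 to 0 | 7 to 1 | 1 - 7 = -6 | less impairment, the most possible | impairment |
| 2 to 4 | 3 to 5 | 5 - 3 = +2 | more impairment | by implication, improvement |
| 0 to 6 | 1 to 7 | 7 - 1 = +6 | more impairment, the most possible | by implication, improvement |

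The stated rule is reversed in every row.

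**Step 4. How many results it touches.** Child Form: 1 total + 4 domains = 5. Parent Form: 1 total + 3 domains = 4. That makes 5 + 4 = 9 score changes. The summaries by response status also show change for single items (24 on the Child Form; 26 or 30 on the Parent Form, depending on age), and the same reversal applies to those if the sentence is taken to cover them.

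**Step 5. Could another rule rescue the sentence?** It would be true if FAQLQ change were Baseline minus Month 12, or if the scores were inverted. Neither document provides for either. Where the SAP wants an item turned round, as in the Food Allergy Independent Measure (FAIM) Parent Form, it says so: "In both scores item 4 needs to be reverse scored". SAP 4.13, which lists departures from the protocol, mentions FAQLQ only to add analysis by domain and by item.

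**The case against.** The strongest reply is that the sentence is a gloss that no program uses. Scores, changes, ANCOVA estimates and p-values come out the same whether it is there or not. FAQLQ is listed among the other efficacy endpoints in SAP 3.2 and does not appear in the 14-step order of SAP Table 2. For such endpoints, protocol 8.5.4 says "No further adjustments will be made for the other efficacy endpoints for which p-values will be provided for descriptive purpose only". Baseline and Month 12 values are tabulated beside the change, and the correct direction can be worked out from the preceding sentence and SAP 4.2, so a careful reader would probably notice. The table shells are in a separate document, so whether the error reaches any output is unknown.

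All of that stands, and it limits the seriousness of the point. It does not make the sentence right: a stated rule of interpretation in the current analysis section should agree with the scale and formula beside it.

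Two narrower points are also fair. The Child Form direction rests on the order of its labels and on the SAP's description of the scale, because the form prints no numeric anchors. And the absence of a stated FAQLQ reversal is supporting evidence only: the FAIM text says that some items need reversing but names none for its Child Form, so the SAP is not fully explicit about reversals. Neither point changes the sign.

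**Conclusion.** The sentence is wrong as written. Under the SAP's own scale direction, coding and change formula, a negative FAQLQ change is improvement and a positive one is worsening, over a possible range of -6 to +6.

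No computed value changes. What is reversed is the reading of nine score changes, and of the item-level changes where these are shown. The primary and secondary conclusions are unaffected. The finding rests on two assumptions: that the SAP 4.2 formula applies to FAQLQ, as its wording for any parameter implies, and that scores are not inverted in some step the SAP does not describe. It should be corrected, but it does not threaten the trial's main inference.

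**What to change.** Replace the sentence in SAP 4.8.4.3 with: *Higher scores mean greater impairment; a negative change from baseline means improvement.* Use the same statement of direction in the footnotes of every FAQLQ change table and plot and in the report text, and check the table shells for any note that copies the present wording.

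Defining FAQLQ change as Baseline minus Month 12 would also remove the contradiction, but it would depart from the SAP 4.2 convention and flip the sign of every FAQLQ change produced. Correcting the sentence is simpler.

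The cost is one sentence in the SAP and a review of footnotes. No score or model needs reprogramming.
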